1 PROTOCOL SUMMARY

1.1 SYNOPSIS

Grant Number:

Study Description:

Title:

The Impacts of Predictable Income Volatility and Income **Risk on Economic Outcomes and Behaviors** 1R01AG076655 To explore the relationship between income stability and health, we will run a randomized experiment in northern Ghana. To accomplish this goal, the study will provide temporary employment for low-income individuals during the lean season, when work is scarce. Participants will be randomly assigned to one of the four arms which vary whether the number of work hours vary over time and whether they vary predictably or unpredictably. The study will enroll 2,267 participants for 12 weeks (i.e. 6 periods) with an additional follow-up survey occurring 4 weeks after the conclusion of the active study phase. We hypothesize that all treated participants will experience gains in mental health relative to the control (given the increased income), but that the gains will be largest among the arm receiving stable and predictable work and lowest in the arm receiving unstable and unpredictable work.

Objectives*:

Primary Objective:

1) Identify the causal effect of income instability on psychological health (e.g. depression, anxiety), biomarkers of stress (e.g. cortisol), and physical health (e.g. blood pressure).

Secondary Objectives:

- 1) Decompose the effects identified in aim 1 into the effects of predictable and unpredictable income instability and compare them to the impact of increasing the average level of income.
- 2) Investigate the channels through which effects on health occur, including both economic and behavioral channels and estimate the impact of key moderating factors (e.g. age, gender, baseline mental health).

Endpoints*:

Primary Endpoint:

- 1) Depression
- 2) Anxiety
- 3) Stress cortisol
- 4) blood pressure
- 5) dietary diversity and sufficiency

Secondary Endpoints:

- 1) Stress self-reported
- 2) Worry
- 3) Subjective-wellbeing
- 4) Weight

The study will take place in communities/districts around Tamale in the Northern Region of Ghana. A random sample of households will be surveyed in approximately 135 villages to identify eligible participants.

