4 STUDY DESIGN

4.1 OVERALL DESIGN

The study will consist of a 4- arm phase-3 randomized controlled trial to avoid concerns around the measurement and endogeneity of income streams and participants knowledge of those income streams. We hypothesize that the impact of the treatments on our primary endpoints will be positive overall (due to the increased work and income), but that the Stable Income will have the largest treatment effects, the Predictable Volatility arm the next largest, and the Unpredictable Instability arm the least (though still positive relative to the control).

The randomization will be at the individual level, stratified by village. Participants will be randomized among 4 arms:

1) The Control Arm: The Control arm will not be hired by the cash-for-work program but will be surveyed;

2) The Stable Income Arm: The Stable Income arm will work the same number of days and earn the same amount every two-week period;

3) The Predictable Instability Arm: The work days and earnings of the Predictable Instability arm will vary over time. In three periods, the participant will work more days and will earn more. In the remaining three periods, she will work fewer days and will earn less. Crucially, she will be able to predict all swings in her study earnings in the future—i.e., she will know her work days and earnings in each future two-week period.

4) The Unpredictable Instability Arm: The work days and earnings of the Unpredictable Instability arm will vary unpredictably over time. In any given two-week period, there will be a 50% chance that she works more days and earns more and a 50% chance that she works fewer days and earns less.

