5.5 STRATEGIES FOR RECRUITMENT AND RETENTION

We expect to screen roughly 10,000 households to reach our enrollment target of 2,267 participants. Households to be screened will be determined by a random sampling procedure within the targeted villages until the target number of households is reached. The target number of households per village will be a function of the village size, to ensure a relatively sparse randomization. These interviews will be conducted in person as in-person data collection will result in more accurate screening data and avoid any concerns around unreliable cell service and limited literacy. All of these households will be located in the vicinity of Tamale, Ghana. Local enumerators who are fluent in the local dialects and familiar with these areas will be enlisted to undertake this screening. Enumerators will not work after dark for their safety in traveling. To ensure participant safety, the interview will take place in a location of the participant's choice near or in their home and the study team will conduct back-checks and flag any discrepancies from protocols for review with a supervisor.

The screening will produce a household roster to identity potentially eligible individuals within the household. Consistent with the inclusion and exclusion criteria of the study, these individuals will be non-pregnant women between 18-65 years old living in (relatively) small households.

This process will result in roughly 2,267 African women between the ages of 18-65 being enrolled into the study (see inclusion/exclusion criteria for justifications for age restrictions).

The household screening survey used to determine eligibility will be conducted over the course of approximately 4-5 weeks in the spring of 2025. We will then enroll all participants in the study in 2-4 weeks in late March to early May of 2025. The pilot study will be conducted in the late spring/early summer of 2024.

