6.3 MEASURES TO MINIMIZE BIAS: RANDOMIZATION AND BLINDING

We will recruit 2,267 participants, randomly assigning 400 to the Control, 400 to the Stable Income, 400 to the Predictable Volatility, and 1,067 to the Unpredictable Instability arm. Among those in the Unpredictable Instability arm, we expect 1/3 to end the study with the same average earnings as those in the Stable or Predictable volatility arm. Roughly 1/3 will earn more overall and roughly 1/3 will earn less overall, given the randomized draws. Participants are not (and cannot be) blind to their condition. The randomization will be conducted using Stata or R following the completion of the screening process. Because not all individuals selected via screening will consent, we will identify "backup" participants in each wave of enrollment to reach our target enrollments. We will stratify the randomization within village to improve power.

2,267 Participants					
400 Control	400 Stable Income	400 Predictable Volatility	1,067 Unpredictable Instability		

The period-by-period randomization for the amount of work received by each participant in the Unpredictable Instability arm will follow the protocol described in Section 4.1.

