9.2 SAMPLE SIZE DETERMINATION

Given IPAs' performance on similar previous surveys during the lean season (when respondents are relatively available), we assume a uniform 5% attrition across all arms.

We will recruit 2,267 participants. 1,067 will be assigned to the Unpredictable Instability arm and 400 to each one of the other three study arms. About 37.5% of the Unpredictable Instability arm (i.e., 400 individuals) are expected to have Neutral 4-period schedules, such that the estimation of the effect of ex-ante income uncertainty corresponds to a randomized controlled trial with a sample size of 760 (95% of 800) equally split between "treatment" and "control". For a two-tailed test with 0.05 significance level and 0.8 power, the minimum detectable effect (MDE) is 0.2 of a standard deviation (SD) for each primary outcome (calculations done in Stata). These effect sizes are consistent with those found in the literature on the effects of cash transfers in low-income settings (e.g., Haushofer & Shapiro, 2016 & 2018; McIntosh & Zeitlin, 2020). Similarly, the MDE for the effect of predictable income volatility is also 0.2 SD. The estimation of the effect of income risk, which corresponds to RCT where 72.7% of the 1,394 (95% of 1,467) participants are assigned to the treatment condition, has an MDE of 0.17 SD. The estimation of the effect of income realizations has an MDE of 0.19 SD if those with unlucky and lucky schedules are grouped together and of 0.23 SD if they are each compared separately to those with Neutral schedules. For panel data analyses, standard errors will be clustered at the individual level (the unit of randomization) (Abadie et al. 2017). These are conservative estimates that consider data from the follow-up survey only; they ignore that we will have baseline measures of all outcomes of interest, which should substantially reduce MDEs, and that we will have repeated measures of most outcomes. In addition to an index of mental health, given the rapid evolution of multiple hypothesis testing techniques, will we use state of the art techniques to adjust for multiple hypothesis testing.

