9.4 STATISTICAL ANALYSES

9.4.1 GENERAL APPROACH

To study the effects of uncertainty, we will compare the outcomes of participants assigned to the Unpredictable Instability arm to the outcomes of participants assigned to the Predictable Instability arm, while holding the payment schedule constant. Similarly, to study the effects of predictable income volatility, we will compare the outcomes of participants assigned to the Predictable Instability arm to the outcomes of participants assigned to the Stable Income arm. Finally, we will estimate the effects of a stable income by comparing the outcomes of participants assigned to the Control arm.

For each of the individual outcomes, the primary regression model will be:

$$Y_{it} = \lambda_0 + \sum_{\{k=1\}}^3 \lambda_1^k T_i^k + \lambda_2 X_i + \lambda_3 Y_{i0} + \gamma_t + \epsilon_{it}.$$

where *i* indexes the individual; Y_i is individual *i*'s outcome in the post-treatment period *t*; T_i^k is an indicator for treatment arm k; X_i is a vector of individual-level controls (e.g., age); Y_{i0} is the dependent variable at baseline; and; ϵ_i is the error term. Period fixed effects (γ_t) are also included to control for period effects. The analysis considers treatment assignment as the independent variable, regardless of compliance (i.e., intent-to-treat). We utilize an ANCOVA regression model. Standard errors are clustered by individual. λ_1 are the key coefficients of interest and can be interpreted as the causal effect of each treatment relative to the control group. Additional comparisons between treatments will be conducted to parse the impacts of predictable and unpredictable volatility. Also, to study if outcomes fluctuate together with income, we will compare participants from a given arm with different current study earnings (but who had identical earnings in the past). Given the rapid evolution of multiple hypothesis testing.

A pre-analysis plan will be registered after the pilot but prior to the main study with any updates to this analysis plan based on learnings from the pilot.

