9.4.3 ANALYSIS OF THE SECONDARY ENDPOINT(S)

Secondary endpoints are not dependent on primary outcomes but rely on standardized scales for mental health measures. Weight will be measured in kilograms. We will examine both absolute

changes in the weight level as well as percentage changes in weight. Economic measures will generally be measured in local currency to allow for standardization. Secondary measures are also generally repeated, with the exception of weight which is only captured at baseline and endline The same regression approach will be used for secondary outcomes as described above for primary outcomes.

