9.4.7 SUB-GROUP ANALYSES

While there are reasons to expect that the effects of income instability may vary with age, we are not aware of any prior evidence that strongly suggests the effects may vary by race or ethnicity. Nonetheless, because these effects are of interest, we will augment our primary regression specification – detailed above – to study heterogeneous treatment effects along a number of key dimensions. This analysis will include the covariate of interest (main effect) and its interaction with each of the treatment dummies (interaction effects) to assess which individuals are affected the most by income instability. This is a standard and unbiased statistical analysis to compare whether covariates of interest modify the effects of income instability. This assessment will include baseline covariates likely to moderate the impact of the instability (including age, baseline levels of psychological health and of assets). Given the racial homogeneity of the anticipated study population, no heterogeneity analysis is planned for racial differences at this time.

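### Allocation is stratified by village to gain power, but the 9.4.1 model names no village term, so the reported full-arm standard errors are somewhat too wide

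*Combined protocol and SAP*

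**What the plan says.** On design, section 4.1 states: "The randomization will be at the individual level, stratified by village". Section 6.3 gives the purpose: "We will stratify the randomization within village to improve power". The synopsis puts the number of strata at about 135: "A random sample of households will be surveyed in approximately 135 villages to identify eligible participants". Villages will contribute unequal numbers, because under 5.5 "The target number of households per village will be a function of the village size".

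On analysis, the regression in 9.4.1 contains three arm indicators, a covariate vector, the baseline value of the outcome and period fixed effects, with standard errors clustered by individual. The covariate vector "is a vector of individual-level controls (e.g., age" being its one example. Section 9.4.2 applies this model to the primary endpoints. Section 9.4.3 says "The same regression approach will be used for secondary outcomes as described above for primary outcomes", and for heterogeneity 9.4.7 says "we will augment our primary regression specification". Village does not appear in any of these models. Section 9.4.1 also promises a pre-analysis plan, to be registered between the pilot and the main study.

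**The concern.** Stratifying by village forces the arms to be nearly balanced within each village, so differences between villages largely cancel out of a comparison of whole arms. The true sampling variance of the contrast falls whether or not village is in the model. The estimated variance falls only if village is in the model. Otherwise the between-village variation stays in the residual, and the reported standard error is close to what an unstratified trial would give. Clustering by individual handles repeated measures on one woman and does nothing about this.

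At stake is power. The full-arm contrasts are sized close to the margin (power about 0.787 for 0.2 SD, shown below) before the promised multiplicity adjustment, so part of the gain that 6.3 seeks would go unused. The choice also affects every full-arm standard error and p-value, and the plan leaves it undeclared.

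**Working it through.** **Inputs.** From 9.2: allocation 400/400/400/1,067, 5% attrition, two-sided 0.05, power 0.80. From the synopsis: about 135 villages. This gives 2,267/135 = 16.8 women per village, about 3 per 400-woman arm and about 7.9 in the Unpredictable arm. After attrition, 380 women remain in each smaller arm, about 1,013 in the Unpredictable arm and about 2,154 in all. The residual village ICC (after baseline adjustment) is not in the documents. I assume 0.02, 0.05, 0.10 and 0.20.

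**Step 1: the plan's own figures.** With SD = 1, MDE = (1.96 + 0.8416) × sqrt(1/n1 + 1/n2).
- Predictable v Stable: 2.8016 × sqrt(2/380) = 2.8016 × 0.0725 = 0.203 (stated 0.2).
- Income risk: 2.8016 × sqrt(1/380 + 1/1,013) = 0.169 (stated 0.17).
- Power for 0.2 SD with 380 per arm: 0.787.

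The stated MDEs reproduce and take no credit for stratification, so this point does not affect them.

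**Step 2: upper bound.** With exact balance in every village, the true standard error is the unstratified one times sqrt(1 - ICC). The excess width without village terms is then 1/sqrt(1 - ICC) - 1, that is 1%, 3%, 5% and 12% at the four ICCs.

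**Step 3: simulation with realistic imbalance.** The setting is 135 villages and exact arm totals. Each village receives the whole-number part of each arm's share, with remainders placed at random. Loss is 5%, with a single endline, robust standard errors and 10,004 replicates per ICC. The contrast is Predictable v Stable.

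| Residual ICC | Reported SE, no village terms | Reported SE, village effects | True SD, no village terms | Excess width, no village terms | Power for 0.2 SD, without v with |
|---|---|---|---|---|---|
| 0 | 0.0725 | 0.0732 | | | |
| 0.02 | 0.0725 | 0.0724 | | about 1% | 0.783 v 0.782 |
| 0.05 | 0.0725 | 0.0714 | 0.0719 | 1% | 0.782 v 0.792 |
| 0.10 | 0.0725 | 0.0695 | 0.0704 | 3% | 0.796 v 0.821 |
| 0.20 | 0.0724 | 0.0655 | 0.0672 | 8% | 0.810 v 0.868 |

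Excess width is reported SE over true SD, for example 0.0724/0.0672 = 1.077. Type I error without village terms was 0.044 at ICC 0.10 and 0.035 at 0.20; with village effects it was 0.052 at both. As a hand check on the third column, 0.0732 × sqrt(1 - ICC) gives 0.0714, 0.0694 and 0.0655 at ICC 0.05, 0.10 and 0.20.

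The loss lies mainly in the reported standard error. True SDs without v with village effects are 0.0719 v 0.0717 at ICC 0.05 and 0.0672 v 0.0655 at 0.20. With village sizes varying (assumed coefficient of variation 0.5), power was 0.792 v 0.797, 0.792 v 0.817 and 0.809 v 0.864 at ICC 0.05, 0.10 and 0.20.

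**Step 4: is stratification the cause?** In a separately coded run without attrition (3,000 replicates), the ratio of reported SE to true SD without village terms was 1.07 at ICC 0.10. With unstratified allocation at the same ICC it was 1.00.

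**Step 5: the calendar-matched contrast.** For this contrast 9.2 says "the effect of ex-ante income uncertainty corresponds to a randomized controlled trial with a sample size of 760". That is 760/135 = 5.6 women per village, and 134 village terms would use 134/760, about 18%, of the sample.

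| Residual ICC | No village terms | Village effects on the subset | Village effects in the pooled all-arm model |
|---|---|---|---|
| 0 | 0.0726 | 0.0761 | 0.0737 |
| 0.02 | 0.0725 | 0.0753 | 0.0729 |
| 0.05 | 0.0725 | 0.0741 | 0.0718 |
| 0.10 | 0.0725 | 0.0722 | 0.0699 |

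Fitting village effects on the subset alone costs precision up to ICC 0.05 and gains almost nothing at 0.10. Comparisons within the arm among women with the same history are sparser still: after three draws, 1,067/8 = 133 women, about one per village.

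**The case against.** The strongest case is that this is an open detail with a small and uncertain effect.

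- **The covariate list is illustrative, and a pre-analysis plan is still to come.** Village terms are therefore not ruled out. But village indicators are not individual-level controls, the stratification is already known and does not depend on the pilot, and no text commits to including them.
- **The size depends on an ICC that nobody has stated.** This stands. At zero, village effects cost about 1% of the standard error; at 0.02 there is nothing to gain. Nothing in the documents supports 0.20 in particular.
- **The small excesses are near simulation noise.** This also stands. With 10,004 replicates the relative error of a simulated SD is about 1/sqrt(2 × 10,004) = 0.7%, so the figures at 0.02 and 0.05 cannot be told from zero. Other runs at ICC 0.20 gave between about 5% and 11%.
- **Balance could be weaker than simulated.** Backups (6.3) and replacements (7.2) are not said to come from the same village and arm. Filling a quarter of slots from other villages (an assumption) cut the excess at ICC 0.20 to about 3%. The direction did not change.
- **The simulation uses one endline, whereas the plan fits a panel.** In a balanced panel with regressors fixed over time, the regression reduces to one on person means, so the mechanism carries over. The relevant ICC is then that of the person mean, and the power figures above are not those of the panel model.

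**Conclusion.** The concern holds. Followed as written, 9.4.1 reports standard errors for full-arm contrasts that ignore the stratification, and 9.4.2, 9.4.3 and 9.4.7 inherit this. Intervals and tests are conservative wherever the residual between-village variance is appreciable. There is no bias and no inflation of type I error.

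The size is modest. It is negligible at a residual ICC of 0.02, about one power point or less at 0.05, about 2.5 points at 0.10 and nearly 6 at 0.20. These figures rest on assumed ICCs, near-balance within villages, 5% loss and a single endline. The conclusion does not extend to the calendar-matched and same-history comparisons in the same way, because the envelope draws that define those groups are not described as stratified by village. The change is worth making because it is nearly free and settles an undeclared analysis choice; the trial's validity does not depend on it.

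**What to change.** State in 9.4.1, or in the pre-analysis plan before the main study starts, that village (stratum) fixed effects enter the model fitted on all four arms, and the secondary and subgroup models that reuse it. Keep the individual-clustered robust standard errors.

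For the calendar-matched uncertainty contrast and the same-arm, same-history comparisons, say that village effects will not be fitted on the sparse subset alone. Either estimate these contrasts inside the pooled all-arm model with village effects or leave village out. Both are defensible; name one in advance so that the choice is not left to the analyst.

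**Cost.** About 134 degrees of freedom among about 2,154 women (134/2,154 = 6%). If the residual ICC is truly zero, the full-arm standard error rises from 0.0725 to 0.0732, about 1%. For the calendar-matched contrast, the pooled version costs 0.0737/0.0726, about 1.5%, in the same case. No extra data or enrolment is needed.

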9.4.2 ANALYSIS OF THE PRIMARY ENDPOINT(S)

We will use the standardized scoring approaches to all mental health outcomes, including any reversals of scale items as needed. These measures are repeated as described in the timelines previously.

ANCOVA regressions, as outlined in section 9.4.1 above, will be run to analyze the differences between experimental arms. Standard errors will be clustered by individual in all panel regressions. Results will be presented in a regression table with point estimates and standard errors. The regressions will be intention to treat (ITT) with all available data. Data will be cleaned to winsorize outliers, but no imputation will be conducted. If attrition is imbalanced, bounding exercises will be conducted. Given the rapid evolution of multiple hypothesis testing techniques, will we use state of the art techniques to adjust for multiple hypothesis testing.

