Income instability may also harm the psychological health of the poor. The uncertainty about whether and when income will dip and if and how they will manage to make through may cause anxiety, worry, and stress (Dobridge 2018; Carleton et al. 2007; MacLeod et al. 1991; De Berker et al. 2016). The prospect of deprivation experienced when income dips is a threat. Anxiety is a response to a potential threat about which there is uncertainty (Carleton et al. 2007). Uncertainty also underlies worry, defined by MacLeod et al. (1991) as a cognitive phenomenon "concerned with future events where there is uncertainty about the outcome." Similarly, the uncertainty about whether one will be capable of coping with such a change in environmental demands may cause stress (Cohen et al. 1997).

The uncertainty associated with income instability may ultimately accelerate cellular aging and the progress of age-related diseases. In "Uncertainty and Stress: Why it Causes Diseases and How it is Mastered by the Brain" (Peters et al. 2017), Bruce McEwen and co-authors argue that stress arises when one is uncertain about how to safeguard one's future physical, mental, and social wellbeing and that this stress in turn burdens the body with "allostatic load", "the wear and tear on the body" that accumulates as an individual is exposed to repeated or chronic stress (McEwen & Stellar 1993). When acute stress responses are insufficient for resolving uncertainty, "the neuroendocrine, cardiovascular, neuroenergetic, and emotional responses become persistently activated so that blood flow turbulences in the coronary and cerebral arteries, high blood pressure, atherogenesis, cognitive dysfunction and depressed mood accelerate disease progression" (Peters et al. 2017, p.167).

This reaction may cause a vicious cycle as one ages. The glucocorticoid cascade hypothesis argues that aging causes degenerative changes in the region of the brain responsible for shutting off the

stress response (Sapolsky et al. 1986). When this response is not promptly turned off, it causes further damage to the brain. Hence, uncertainty could trigger a circular process where stress accelerates aging, in turn damaging an individual's capability to cope with the effects of uncertainty, further exposing her to the effects of allostatic load (Peters et al. 2017).

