Randomization will be done using statistical software for the treatment assignments and a process of drawing sealed envelopes for the period-by-period realizations in the Unpredictable Instability arm (to increase trust in the randomization process). The Control, Stable, Predictable Volatility arms will each have 400 participants. The Unpredictable Instability arm is overweighted with 1,067 participants, as the analysis of this arm will be disaggregated depending on the draws realized by each participant. The participant will learn of their study arm assignment after consent and the baseline survey, but prior to the beginning of the first 2-week period. The PIs and associated staff under their direction will generate the randomization code and output, with the exception of the period-by-period draws for the Unpredictable Instability participants which will occur in the field.

Unpredictable Instability participants will realize their draw for the next period in the five days between the time when the work for the prior period is completed and the work for the next period begins. This randomization is assured to be truly random via the following procedure:

- The field officer arrives at the participant's house with two sealed envelopes. One contains a "high" draw and the other a "low" draw for the period, as indicated by a work calendar. Both have the participant's ID number on the outside of the reverse (sealed) side of the envelope.
- The participant selects and opens one envelope
- The field officer photographs the calendar from the open envelope in the same frame as the sealed envelope with the same participant ID. This ensures that we can verify which envelope was opened first, and hence the draw of the participant for that period.
- The participant then opens the second envelope to verify that it held the other type of calendar/draw.

While we do not anticipate having randomization errors, should they occur, we will drop those participants from the study.

Each participant will be enrolled for 6 2-week periods. In addition, they will respond to an eligibility survey roughly 2-4 weeks prior to enrollment and complete a follow-up survey 1 month following the end of the active study period.

All participants will be enrolled from a single site surrounding Tamale, Ghana.

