Effect of Ex-Ante Income Uncertainty. We will estimate *ex-ante* income uncertainty by comparing Unpredictable Instability and Predictable Instability participants with *identical earnings profiles over time.* E.g., we will compare the Unpredictable Instability participants to the Predictable Instability participants. They had identical profiles over the first 4 periods. But, the Predictable Instability participant knew these income swings in advance while the Unpredictable Instability participant did not. The comparison is internally valid because the earnings profile for the Unpredictable Instability participant is randomly determined. To compensate for using a subsample of the arm, more individuals will be assigned to it.

Effect of Income	Table 4: Group Comparisons and the Effects They Estimate			
estimate the effect of	Comparison of	Estimates Effect of		
income realizations	Stable Income to Control	Level of Income		
(what actually happened) by	Predictable Instability to Stable Income	Predictable Instability		
comparing	Unpredictable Instability to Predictable Instability	Unpredictable Instability		
Unpredictable Instability	Unpredictable Instability and Predictable Instability with Identical Earnings Profiles over Time	Ex-Ante Income Uncertainty		
participants who by chance end up with	Unpredictable Instability w/ Diff. Income Realizations	Ex-Post Income Realizations		

different income realizations.

Justification of the Control: For our study we will randomly select individuals from those determined to be eligible to serve as an internal control group for comparison as there may be significant time trends in this population given the progression through the lean season. These individuals will be surveyed following the same timeline as all other participants, but not participate in the work program. Given that our sample density is less than five percent in any selected village, we do not anticipate spillovers from randomly sampled individuals in treatment arms to or from individuals in the control arm.

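### Section 9.2's n = 760 and 0.2 SD for the ex-ante uncertainty contrast rest on a four-period match, but three of the five primary outcomes and the full PHQ-8 and GAD-7 are read only after period 6

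*Combined protocol and SAP*

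**What the plan says.** Under sections 4.1 and 6.1.1 there are six two-week periods. Each Predictable participant has three high and three low periods. Each Unpredictable participant has an even chance of high or low in every period. On timing, "Unpredictable Instability participants will realize their draw for the next period in the five days" that separate one period's work from the next, so all six draws are known by the end of period 6.

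Section 4.2 estimates ex-ante uncertainty by comparing Unpredictable and Predictable participants whose earnings followed the same path. Of its example pair it says: "They had identical profiles over the first 4 periods". Section 9.4.1 makes the same comparison "while holding the payment schedule constant".

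Section 9.2 gives the size: "About 37.5% of the Unpredictable Instability arm (i.e., 400 individuals) are expected to have Neutral 4-period schedules". These 400, set against the 400 Predictable participants, make 760 after 5% attrition, and "the minimum detectable effect (MDE) is 0.2 of a standard deviation (SD) for each primary outcome". The same section says its MDEs rest on the follow-up survey alone and does not say which survey that is. Section 6.3 gives a different share for the end of the trial: "we expect 1/3 to end the study with the same average earnings as those in the Stable or Predictable volatility arm".

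In section 1.3, psychological measures are Full at baseline and after period 6 and Short in the other rounds. Blood pressure, diet and weight appear at baseline, after period 6 and four weeks later. Section 8.1 lists PHQ-2 and PHQ-8, GAD-2 and GAD-7, and has hair for cortisol collected at home. On scoring, section 9.4.2 says: "We will use the standardized scoring approaches to all mental health outcomes, including any reversals of scale items as needed".

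**The concern.** The 760 exists only while the four-period match holds. By either survey that could be the follow-up, two more draws have been made, and many of the 400 no longer share an earnings path with a Predictable participant. The claim for every primary outcome therefore joins a sample defined at period 4 to outcomes mostly read after period 6.

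This is the contrast for which the Unpredictable arm was enlarged to 1,067 (section 4.2). If the matched sample is smaller than stated, a null result would be read against a detectable effect that the design does not deliver.

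Timing also affects meaning. The background holds that "Anxiety is a response to a potential threat about which there is uncertainty", and after period 6 no study draw is outstanding. A reading at period 4 and one at endline are not interchangeable, so the plan should say which one its sample size belongs to.

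**Working it through.** **Inputs.** Section 9.2: 1,067 Unpredictable and 400 Predictable participants, 5% attrition, two-sided 0.05, power 0.80. Section 4.1: six periods, even odds per draw, three high and three low in the Predictable arm.

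**Formulas**, outcome SD = 1. MDE = (1.960 + 0.842) × √(1/n₁ + 1/n₂) = 2.8016 × √(1/n₁ + 1/n₂). Power at effect d = Φ(d/√(1/n₁ + 1/n₂) − 1.960).

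1. *The plan's figure.* Balanced over four periods: C(4,2)/2⁴ = 6/16 = 37.5%; × 1,067 = 400; × 0.95 = 380. With 380 v 380, MDE = 2.8016 × √(2/380) = 0.203 SD, and power at 0.20 SD is 78.7%. The stated 0.2 reproduces on the four-period basis.

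2. *Which primary outcomes have a reading at the end of period 4?* That is about week 8, Day 52–56. The schedule column headed 4 shows Day 38–42; both rounds are Short phone rounds. Blood pressure and diet have no entry there. Cortisol sits in the psychological row, but hair collected at home cannot be obtained by phone. PHQ-8 and GAD-7 belong to the Full rounds. That phone rounds carry the two-item forms is an inference. For PHQ-2 it is supported by the referral rule, which applies a PHQ-2 threshold (sections 2.3.1 and 8.2) to the twice-monthly surveys (2.3.1). So three of the five primary outcomes, and the full forms of the other two, have their post-baseline readings only after period 6.

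3. *What becomes of the 400.* One high and one low draw in periods 5–6 has probability 2/4. Half stay balanced (200); the other half have had two highs or two lows.

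4. *Match after period 6, reading A: Predictable schedules span all balanced six-period paths.* C(6,3)/2⁶ = 20/64 = 31.25%; × 1,067 = 333; × 0.95 = 317. This fits the one-third in section 6.3. With 317 v 380, MDE = 2.8016 × √(1/317 + 1/380) = 0.213 SD; power at 0.20 SD = 74.8%.

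5. *Match after period 6, reading B: every Predictable schedule is balanced over the first four periods.* Each must then also be balanced over periods 5–6. The share is 0.375 × 0.5 = 18.75%; × 1,067 = 200; × 0.95 = 190. An Unpredictable path such as HHHLLL is balanced over six periods but has no identical Predictable partner. With 190 v 380, MDE = 2.8016 × √(1/190 + 1/380) = 0.249 SD; power at 0.20 SD = 61.5%.

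6. *Which reading fits 9.2?* Its 400 v 400 split uses the whole Predictable arm as the match for four-period balance, which is reading B. Under A with paths spread evenly, only 12 of the 20 balanced paths are balanced over four periods: 12/20 × 400 = 240 Predictable participants, not 400.

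**The case against.** The ex-ante contrast serves a secondary objective. The stated primary model compares each arm with control in everyone randomized, and nothing here touches that. This stands and limits the reach of the point. Section 9.2 nevertheless makes this contrast its leading calculation.

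Section 9.2 calls its figures conservative, because they ignore baseline values and repeated measures. This also stands in part. Baseline adjustment multiplies the MDE by √(1 − ρ²). Under reading B, bringing 0.249 back to 0.203 needs 1 − ρ² = (2/380)/(3/380) = 2/3, so ρ of about 0.58. The documents give no correlation, and an adjusted gain does not make the stated n correct.

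All 400 could be kept at endline despite periods 5–6. But half would then have had two highs or two lows, so ex-ante uncertainty would be mixed with income realizations, which section 4.2 treats as a separate effect.

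A pre-analysis plan is promised and may settle this. It is not among the documents.

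Three stronger readings are tempting and not supported:
- *That 9.2 makes the two-item forms primary.* It applies its MDE to every primary outcome, including three with no period-4 reading, so it does not point to a form.
- *That the analysis sections give no rounds or baseline.* Section 9.4.1 sets out a panel over post-treatment periods with period effects and adjusts for the outcome's baseline value; 9.4.2 uses all available data. Only the form in each round is open.
- *That short and full raw scores will be pooled, or that a bias or inflated error rate is shown.* Pooling is not stated, and neither harm is demonstrated.

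**Conclusion.** The point holds as a mismatch within section 9.2 and with the schedule. The arithmetic behind 0.2 SD is right for a four-period match. It does not apply to outcomes read after period 6, where the matched contrast has an MDE of 0.213 SD (317 v 380) or 0.249 SD (190 v 380), with power of 75% or 61% at 0.20 SD. Which applies depends on the Predictable schedule set, which the documents do not state; the equal split in 9.2 implies the second.

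These figures assume even odds at each draw, 5% attrition in both groups, exact path matching, and no gain from baseline or repeated measures, as in 9.2. Reading A also assumes similar path mixes in the two groups, or no loss from reweighting. The effect of moving between two-item and full forms cannot be sized, because the documents give no SD, reliability or between-form correlation.

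**What to change.** In section 9.2:
- Restate n and MDE of the ex-ante contrast on six-period schedules for outcomes read after period 6.
- State which set of Predictable schedules is assumed.
- Say which survey the follow-up figures refer to.
- Limit 760 and 0.2 SD to outcomes measured by the end of period 4.

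The cost is wording and a less favourable stated figure. No visit, item or participant is added.

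As a minor clarification, in section 9.4.2 or the pre-analysis plan: name which PHQ and GAD form enters in each round, adjust for the same form at baseline, and do not put two-item and full-form raw scores in one regression. Which form is primary is the sponsor's choice; each has a cost in timing or precision.
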